The PINNACLE Registry® is the largest outpatient cardiovascular clinical data registry in the world, with millions of patients drawn from thousands of sites around the US representing over 10,000 outpatient providers. The registry has a comprehensive goal of improved patient care. In addition to using the PINNACLE Registry®, non-PINNACLE sites within large health systems will be recruited and randomized into the intervention and usual care arms respectively.

[figure not shown]
The Specific Aims of this study will be:

- To evaluate ability of ACC Solution Sets and Patient Resources to improve initiation and titration
 of GDMT for eligible patients with HFrEF Left Ventricle Ejection Fraction (LVEF) ≤ 40%.
- To evaluate change in QOL between patients in the Intervention arm and the Usual Care arm.
- Examine relative change in GDMT among higher risk versus lower risk patients in the Intervention arm and Usual Care arm.

In this randomized registry trial, sites will be invited to participate in a 6-month study aimed at various processes of care in HFrEF. Sites would be informed that they might be asked to participate in an intensive intervention to improve GDMT prescription or in a study of QOL in HFrEF. Once a list of sites interested in participating is created, sites would be randomized into two arms: an intervention group and a usual care group.

AMERICAN

(**Figure 1**): This graphic shows both usual care and intervention arm tracts.

Study Population:

- Patients from practices participating in the PINNACLE Registry® (these include those that are
 part of integrated health systems, stand-alone, and other practice environments); as well as
 patients from other practices (these include those that are part of integrated health systems,
 stand-alone, and other practice environments) with pre-existing data interfaces with study
 partner HealthReveal.
- Patient cohorts will have the following **inclusion** criteria:
 - Age ≥18 years
 - Clinical diagnosis of HF with EF ≤40% documented within 1 year of enrollment
 - Receiving ≥1 oral medication for HF at study enrollment (including diuretics, ACEI/ARB/ARNI, beta-blockers, MRA, SGLT2i or thiazide diuretics.
- Patient cohorts will have the following **exclusion** criteria:
 - Current or anticipated participation in a clinical trial
 - Currently receiving comfort care or enrolled in hospice
 - Life expectancy <1 year
 - o History of or plan for heart transplantation or left ventricular assist device

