- Quick Tips series provides guidance on many of the topics that are raised during medical visits, but we may not have sufficient time to go into great detail about; for example, how to record daily weights, stay active, limit sodium, take medications, watch for triggers that can exacerbate heart failure, and pay attention to emotional health and mental outlook

The Usual Care arm, will be managed as close to "true" usual care as possible. To avoid influencing management, once randomized to usual care, other than to collect QOL measures (assessed using the Kansas City Cardiomyopathy Questionnaire-23) at baseline, 3 months, and 6 months, study sites will not be contacted until the study has completed and they will be unaware of allocation to usual care. They will not receive specific pre-visit guidance, and though publicly available, sites will not be specifically provided ACC tools.

B. Data Management

Participating sites submit data using an electronic health record (EHR) system integration (SI) tool, where relevant registry data fields can be extracted from a practice's EHR and is then transmitted to a secure database.

Intervention Arm

Steps include:

Data extraction: Mapped to pre-specified data fields, a data extractor (such as that provided by FIGmd) will extract the EHR data to storage at Veradigm for PINNACLE sites. FigMD has historically provided the data extractor solution for the PINNACLE Registry and provides similar services to multiple medical societies across the United States of America. Data extracted may include the following: age, sex, LVEF, medication list (including doses), and laboratory results (such as basic metabolic panel). For the purposes of the study, data from the local EHR will be extracted on a weekly basis.

Creation of Reveals: Following, a similar extractor will then process data to HealthReveal for non-PINNACLE sites, where a dashboard will be created. This dashboard will include a) lists of eligible patients for the study and b) an update on opportunities for further medication optimization. The latter information will be based on guideline-directed medical targets as articulated in the ACC 2020 Expert Consensus Decision Pathway document on management of HFrEF. The dashboard containing the reveals will be conveyed to the sites.

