KCCQ Symptom Stability Domain: measures recent changes in patients' symptoms; their shortness of breath, fatigue or swelling. It compares patients' frequency of heart failure symptoms at the time of completing the KCCQ with their frequency 2 weeks ago. As a measure of change, it is most interpretable as a baseline assessment of the stability of patients' symptoms at the start of a study and shortly thereafter, as a measure of the acute response to treatment. This domain is not included in the summary scores.

Clinical Summary Score: includes total symptom and physical function scores to correspond with New York Heart Association ("NYHA") Classification.

Overall Summary Score: includes the total symptom, physical function, social limitations and quality of life scores.

The KCCQ-23 data will be blinded and stored until end of trial.

Following completion of usual procedures, the patient will be sent home, and followed up per study protocol at 3 month intervals for up to 3 clinical visits and with as many 'as needed' visits to achieve optimal GDMT. At each visit, the Dashboard will provide updated information focused on opportunities for optimizing GDMT.

Usual Care Arm

In the Usual Care Arm, eligible patients will be identified and sites will be alerted to the roster of patients eligible for study participation. These patients will be offered participation into a study of health status in those with chronic HFrEF and if agreeable they will be consented for inclusion to the study and information recorded. Data extracted may include the following: age, sex, LVEF, medication list (including doses), and laboratory results (such as basic metabolic panel). Following, the KCCQ-23 will be recorded via Medable, as above.

To maintain "usual care" as much as possible and avoid internal contamination bias, the managing site will not be aware the medical management is being monitored and the patient will not receive CardioSmart materials.

Follow up in the Usual Care arm will be at the discretion of the managing site. KCCQ-23 will be recorded remotely via Medable over the 6 months of follow up.

Analytics

At study completion, a data extractor (such as that provided by FIGmd) will extract the EHR data from storage and a data sheet across study visits will be provided to the analytic center at the Massachusetts General Hospital.

Safeguards

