Adult patients ages 18 years and older with heart failure with Left Ventricle Ejection Fraction (LVEF) \leq 40% will be identified via an initial data extraction from interested sites. Participating sites will receive a roster of eligible patients, in order to best plan their enrollment. There will be no discrimination or bias with respect to patient inclusion on the basis of sex, race, or religion.

5. Subject Recruitment and Compensation

Upon identification of eligible patients, members of the clinical team will approach the patient with the offer to participate in a clinical study.

At **Intervention sites**, patients will be presented with the goals of the study, and given time to review the Informed Consent (prepared in their own language). Following, if the patient agrees, consent will be signed and patient included in the trial.

At **Usual Care sites**, patients will be presented with a proposal for periodic HFQoL assessment. If the patient agrees, consent will be signed and patient included in the trial.

No compensation will be offered to patients or families for participation in the registry or study.

6. Consent Process

Study consent will be provided electronically ("e-consent"), using Medable software. Consent materials will be provided with sufficient time for the patient to consider their participation in the study. For patients in the Intervention Arm of the study, consent materials will describe the study procedures, expected risks and expected benefits. For patients in the Usual Care arm, consent materials will only focus on the KCCQ-23. All consent materials will be in the patients' native language.

If the patient agrees to participation in the study, their informed consent will be recorded through e-consent processes with signature stored at Medable.

At any time, patients may withdraw consent. In such a circumstance, patients will be analyzed per intent to treat.

7. Subject's Capacity to Give Legally Effective Consent

Only those patients capable of giving informed consent will be enrolled in the study.

8. Study Interventions

In the Intervention arm, for each study visit, the site will receive a pre-visit assessment of GDMT accompanied by recommended adjustment(s) using information extracted weekly from the sites' EHR.

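### No eligible list is fixed before sites are randomized, and the arms are described with different ways of finding patients, so later-arising or newly treated patients can enter them unequally

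*Protocol*

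**What the plan says.** Section 3 (Design and Procedures) randomizes sites once the interested ones have been listed. Sections 4 and 5 then describe how patients are identified, approached and consented.

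- **Both arms.** Section 4 (Selection of Subjects) says patients "will be identified via an initial data extraction from interested sites", and adds: "Participating sites will receive a roster of eligible patients, in order to best plan their enrollment". Neither sentence names an arm.
- **Intervention arm.** Under B. Data Management, Intervention Arm: "For the purposes of the study, data from the local EHR will be extracted on a weekly basis". The Creation of Reveals step then says: "This dashboard will include a) lists of eligible patients for the study", and names as a second item an update on where medication could be optimized. Enrolment is the next step listed.
- **Usual care arm.** Under B. Data Management, Usual Care Arm, "sites will be alerted to the roster of patients eligible for study participation". No refresh is mentioned. Section 3 says that after randomization, apart from collecting quality-of-life measures, "study sites will not be contacted until the study has completed".
- **Drug criterion.** Under Study Population in section 3: "Receiving ≥1 oral medication for HF at study enrollment". Any listed drug counts, including a diuretic.
- **Timing of prompts.** Section 3 sends recommendations to the intervention site ahead of every appointment a patient has. Section 8 (Study Interventions) ties them to study visits.

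**The concern.** When sites are randomized before patients are identified, the arms are comparable only if patients enter both by the same rule. Here the intervention site has a continuing data feed on the same screen as the list of eligible patients. The usual-care site is described as receiving a roster and then being left alone. A patient diagnosed, or found to have an ejection fraction of 40% or less, some weeks after the start could be shown to an intervention site and never listed for a usual-care site.

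Such patients plausibly have more drug classes still to be started or titrated, so their scores may rise without any prompt. An excess of them in one arm would then show up as a difference in the primary change score with no intervention effect. The planned contrast in section 11 is small, 10% of patients improving against 5%, so even a modest imbalance in who enters could matter. A larger sample would not remove it.

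**Working it through.** The plan gives no figure on this point, so the check is mainly a comparison of the text.

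**Step 1. The arms side by side**

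| Step | Intervention | Usual care |
|---|---|---|
| Site allocation | before patients are enrolled | before patients are enrolled |
| Initial extraction and roster (section 4) | applies | applies |
| Other described source of eligible patients | dashboard fed by weekly extraction | roster alert, refresh not stated |
| Contact after allocation | dashboard during the study | quality-of-life collection only |
| Drug criterion | read at enrolment | read at enrolment |
| Prompts before enrolment | open under section 3; section 8 ties them to study visits | none |

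No section freezes the eligible list on data from before allocation, and none states a common refresh rule. Two routes to unequal entry follow:

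1. *Later-arising patients.* They can appear through the intervention feed, with no described counterpart in usual care.
2. *Prompted drug starts.* A patient on no heart failure drug could be started on one after a prompt and then qualify. This needs prompts to reach patients who are not yet eligible, which no section says.

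**Step 2. Illustration of size**

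From section 11: 5% of usual-care patients increase, 10% of intervention patients increase, 5% decrease in both arms, two-sided rank-sum test at 0.05, 1280 per arm (N = 2560). Assumed, because the documents give neither: *x*, the excess share of such patients among intervention enrollees, and *h*, the percentage of them whose score rises without any intervention effect.

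Spurious difference in the percentage improving: D = x × (h − 5).

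For the test, suppose there is no true effect, decreases stay at 5% in both arms, increases are one step, and clustering is ignored. Moving a proportion D from no change (mid-rank 0.5) to increase (mid-rank 0.975) gives θ − 0.5 = 0.475 × D. With T = 1 − Σp̄³ for ties, where p̄ are the category proportions averaged over the arms:

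z = √(3N) × (θ − 0.5) / √T, and P(false result favouring intervention) = Φ(z − 1.96), nominally 2.5%.

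Worked case, x = 5%, h = 30%: D = 0.05 × 25 = 1.25 points. θ − 0.5 = 0.475 × 0.0125 = 0.00594. T = 1 − (0.05³ + 0.89375³ + 0.05625³) = 0.2858. z = 87.64 × 0.00594 / 0.5346 = 0.97. P = Φ(−0.99) = 16%.

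| x | h | D (points) | P |
|---|---|---|---|
| 2% | 20% | 0.30 | 4.3% |
| 2% | 30% | 0.50 | 5.9% |
| 5% | 20% | 0.75 | 8.5% |
| 5% | 30% | 1.25 | 16% |
| 10% | 20% | 1.50 | 21% |
| 10% | 30% | 2.50 | 48% |
| 10% | 0% | −0.50 | 0.9% |

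The last row shows the opposite direction. If the prompted drug is already in the baseline score, the early gain is not counted as change, and such patients may rise less than others. The bias then works against the intervention.

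**The case against.** The strongest case on the other side is that much of the asymmetry is read into silence.

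- *A reader might infer that usual care gets a one-off list.* The text does not say so. The initial extraction in section 4 covers interested sites generally. Because interested sites are listed before randomization, it could even be a common extraction made before allocation. The no-contact sentence exempts quality-of-life collection, and usual-care sites are in any case alerted to a roster. **This stands:** a one-off list fits the no-contact sentence best, but it remains an inference.
- *A reader might infer that the intervention list is refreshed weekly.* What is weekly is the extraction of record data. In the dashboard sentence, updating attaches to the optimization opportunities, not to the list. That step is also worded for non-PINNACLE sites, so it may not describe the whole arm. **This stands** as a limit on the claim, though a list displayed on a weekly-fed dashboard would naturally change.
- *A reader might infer that the intervention generates its own eligible patients.* The dashboard is described as listing eligible patients, and a patient on no heart failure drug is not one. Since any listed drug qualifies, only wholly untreated patients could be converted, and their own clinician could equally start a drug in usual care. **This stands:** the route is open only because sections 3 and 8 differ on when prompts are given, and it is probably narrow.

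None of this supplies the missing rule. If section 4 was meant as a common list fixed before allocation, the protocol does not say that enrolment is confined to it, and the criterion read at enrolment points the other way.

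**Conclusion.** The concern holds in a limited form. After allocation the arms are described with different ways of finding eligible patients, no list is fixed beforehand, and one entry criterion is read at enrolment. A trial run exactly as written could therefore admit later-arising or newly treated patients unequally.

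Neither the size nor the direction of the bias can be derived from the documents. The illustrated differences of 0.30 to 2.50 points, against a planned 5, depend wholly on the assumed x and h, and the sign can reverse. They show only that a small excess share would be enough to matter for an effect of the planned size.

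A reader might also infer that the new-onset and recently hospitalized subgroups would be almost empty in usual care. The documents do not support that: an initial roster can already hold such patients, since the ejection fraction need only have been documented within the past year.

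The change is worth making because it is cheap and removes an avoidable post-allocation selection.

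**What to change.** 1. Run the section 4 extraction at all interested sites before randomization. Apply every extractable criterion at that date, including ejection fraction and at least one heart failure drug. Freeze the list and enrol only from it in both arms.
2. If later patients are wanted, refresh both arms' rosters on the same calendar with the same query, apply the drug criterion before any recommendation is shown, and add that contact as an exception to the no-contact sentence in section 3.
3. Reconcile sections 3 and 8 on which visits trigger recommendations, so that the start of prompts relative to enrolment and baseline is unambiguous.

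Cost: protocol wording and one common query, built on an extraction already planned. With a frozen list, some late-identified and incident patients are not enrolled, which shrinks the new-onset subgroup in both arms. Option 2 avoids most of that loss at the price of some contact with usual-care sites.

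### Patients are enrolled after their site is allocated, with a different offer and consent in each arm, so site randomisation does not balance who enters and the stated test does not address it

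*Protocol*

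**What the plan says.** **Allocation.** Protocol section 3 (Design and Procedures) makes the site the unit of randomisation: "Once a list of sites interested in participating is created, sites would be randomized into two arms".

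**Identification.** Section 4 (Selection of Subjects) says that patients "will be identified via an initial data extraction from interested sites", and that sites get a roster to help them plan enrolment. The Data Management text also places identification inside each arm. For usual care it reads "In the Usual Care Arm, eligible patients will be identified and sites will be alerted to the roster of patients eligible for study participation". For the intervention arm, the list of eligible patients sits on the same dashboard as the medication-optimisation opportunities.

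**Approach.** Section 5 says "Upon identification of eligible patients, members of the clinical team will approach the patient with the offer to participate in a clinical study". No order, completeness rule or record of refusals is given.

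**Offer and consent.** At intervention sites, patients are told the study's goals, and the consent material covers procedures, expected risks and expected benefits (sections 5 and 6). At usual-care sites, "patients will be presented with a proposal for periodic HFQoL assessment", and section 6 adds: "For patients in the Usual Care arm, consent materials will only focus on the KCCQ-23". Only patients who agree enter the trial.

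**Analysis.** Section 11 compares the 6-month minus baseline score between arms by a two-sided Wilcoxon rank-sum test at 0.05. It names no covariate or stratum. Intention to treat is mentioned in section 6 only for patients who withdraw consent.

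**The concern.** Randomising sites makes the pools of eligible patients comparable in expectation. It does not do so for the subset who are approached and agree once the arm shapes the invitation. A patient who accepts a programme aimed at optimising heart-failure drugs, with app surveys every week, need not resemble one who accepts three questionnaires.

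The protocol's own background shows why this matters for the primary endpoint. It calls the role of patient factors in GDMT delivery likely substantial, because titration needs diligence and frequent visits. It also reports that age, blood pressure, functional class, renal function and recent hospitalisation are associated with drug use and dose. Arm-specific recruitment could unbalance the same traits. Any resulting difference in score change would be read as an effect of the intervention, or would hide one.

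**Working it through.** **1. Order of events.** No single sentence states that the offer follows allocation, but it must: the offer and the consent content differ by arm, so the arm is known when they are made. The Data Management text likewise describes consent within the usual-care arm. The timing of identification is less clear. Section 4 refers to an initial extraction from interested sites, which is the term section 3 uses for sites on the list before randomisation, while the Data Management text describes lists within arms.

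**2. Inputs (section 11, power paragraph).** Decreases 5% in both arms; increases 5% in usual care and 10% in the intervention arm; two-sided 0.05; 90% power; 1280 per arm.

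**3. Method.** Categories are decrease, no change, increase. Usual care is (0.05, 0.90, 0.05) and intervention is (0.05, 0.90 − x, 0.05 + x).

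- θ = P(T > C) + ½P(T = C). The usual-care mid-rank probability is 0.05 + 0.90/2 = 0.500 for no change and 0.95 + 0.05/2 = 0.975 for an increase. Hence θ − 0.5 = 0.475x.
- Tie-corrected SD = √[(1 − Σp̄³)/12 × 2/n], where p̄ is the average of the two arms.
- Probability of rejecting in favour of the intervention ≈ Φ[(θ − 0.5)/SD − 1.96].

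**4. The plan's own figure.** At x = 0.05 and n = 1280, 0.02375/0.00655 = 3.63 and Φ(1.67) ≈ 0.95. Power is thus about 95%, not 90%; 90% needs 1022 to 1024 per arm. Since 1024/(1 − 0.20) = 1280, the stated figure may already include the 20% loss. This departure is conservative and has no bearing on the present point.

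**5. Hypothetical illustration.** Suppose the intervention does nothing, but selective enrolment raises the intervention group's natural rate of increases by x. The values of x are assumptions; the documents give none.

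| x | θ − 0.5 | SD | z | Rejects favouring intervention | Rejects two-sided (20,000 simulated trials) |
|---|---|---|---|---|---|
| 0 | 0 | 0.00594 | 0 | 2.5% | 4.9% |
| 0.01 | 0.00475 | 0.00607 | 0.78 | 12% | 12% |
| 0.02 | 0.00950 | 0.00619 | 1.53 | 33% | 34% |
| 0.03 | 0.01425 | 0.00632 | 2.26 | 62% | 62% |
| 0.05 | 0.02375 | 0.00655 | 3.63 | 95% | 95% |

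**6. How much selection that implies (further assumptions).** Suppose patients ready for drug changes improve at 10% and others at 2%. The usual-care rate of 5% then implies a ready share of (0.05 − 0.02)/0.08 = 37.5%. An excess of 1, 2 or 3 points needs that share to be higher by 12.5, 25 or 37.5 percentage points (x/0.08). With rates of 15% and 3% the required shifts are 8.3, 16.7 and 25 points (x/0.12).

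**7. The opposite direction.** If the true rates are 5% and 10% but selection lowers the intervention rate by 2 points, the net difference is 3 points. Power then falls from about 95% to about 62%.

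**The case against.** **The protocol has safeguards.** Eligibility criteria are common to both arms. Usual-care sites are not told their allocation or that drug management is being monitored. Classes with a documented contraindication or intolerance leave the denominator, and each patient's own baseline is subtracted. These help, but none decides who agrees to take part. Intervention sites necessarily know their arm, and subtracting baseline does not remove differences in propensity to change, which is the outcome itself.

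**The different offers are deliberate.** They protect usual care from contamination. That is a legitimate aim, so the fix should leave the offers as they are.

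**Covariates may be in a SAP that is not shown.** This stands. Their absence here is not itself a defect, and an adjusted analysis may already be planned. However, baseline covariates correct only for what is measured, and readiness for drug changes is not. The recruitment rule belongs in the protocol and cannot be repaired later in a SAP.

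**Stronger readings that the text does not support.**

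- A reader might infer that clinicians pick whom to approach. The protocol does not say so; it leaves the approach unspecified.
- A reader might infer that patients are identified only after allocation. The initial extraction may come first.
- A reader might infer that the bias favours the intervention. The surveys and self-management tools could equally attract engaged, already well-treated patients with little room to improve.

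**Conclusion.** The concern holds as a design weakness that should be corrected. Arm-specific offers and consent after site allocation can yield enrolled groups that are not comparable in their propensity for drug changes, and the comparison stated in section 11 does not deal with this.

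Neither the size nor the direction can be derived from the protocol. The 12%, 34% and 62% should not be read as the trial's expected false-positive rate. They rest on assumed excesses of 1, 2 and 3 per 100 and treat patients as independent although sites are randomised. They show only that, against a planned difference of 5 per 100, an imbalance of 2 or 3 per 100 would matter. Under the further assumptions in the working, that requires a substantial shift in case mix.

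**What to change.** 1. State that the eligible roster is frozen from the initial extraction before allocation is released.
2. Require the same approach rule in both arms, either all rostered patients or a random order, with a log of patients approached and declined.
3. Report rostered versus enrolled characteristics by arm.
4. Adjust the primary comparison for baseline composite score and number of eligible classes, and say that this handles measured differences only.
5. Where registry permissions allow, add a sensitivity analysis of the primary endpoint, which is derived from the EHR, in all rostered patients. This is the only step that removes differential consent; steps 1 to 4 limit or reveal selection but leave the two offers in place.

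**Cost.** Protocol wording, a short log and two covariates already available from the extracted data. Sites lose some freedom over the order of approach. At usual-care sites the log should be presented as routine enrolment tracking so that allocation stays concealed. Step 5 depends on permission to use data from patients who did not consent, which the protocol does not show.
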